5.0 Donor Selection

- 5.1** Related donor (sibling, parent, offspring, parent or offspring of an HLA identical sibling) 18-75 years of age
- 5.2** At least 40 kilograms body weight
- 5.3** In general good health as determined by the evaluating medical provider
- 5.4** HLA-haploidentical donor/recipient match by at least Class I serologic typing at the A&B locus
- 5.5** Able and willing to undergo apheresis
- 5.6** Not pregnant
- 5.7** Voluntary written consent

6.0 Patient/Donor Enrollment (On Study)

Enrollment onto the study will occur after the patient has signed the patient consent and eligibility is confirmed, but before any treatment has been administered. Any patient signing consent, but not registered in the study, will be recorded as a screen failure in the screening log as detailed in the study's Affiliate Manual.

To be eligible for enrollment to this study, the patient must meet each criteria listed on the eligibility checklist based on the eligibility assessment documented in the patient's medical record. The eligibility checklists (patient - Appendix I,

donor – Appendix - II) can be found under attachments within the study in OnCore.

6.1 Registration with Masonic Cancer Center Clinical Trials Office

Upon completion of the screening evaluation, eligibility checklist and obtaining consent, the site study coordinator or designee will enroll the patient and donor into OnCore. The patient will be considered “on study”. Complete registration information is found in the study’s Affiliate Manual.

OnCore will automatically generate an email alerting key study personnel of the registration.

6.2 Patients Who Do Not Begin Study Treatment

If a patient is registered on study, and is later found not able to begin the preparative regimen (beginning with the first dose of decitabine), for whatever reason, the patient will be removed from study and treated at the physician’s discretion. The patient will be considered a screen/baseline failure and the reason for removal from study will be clearly indicated in OnCore as detailed in the study’s Affiliate Manual. The patient will be replaced.

If a patient begins treatment, and then is discontinued for whatever reason, the patient will be replaced as the clinical response (CR + PR + HI) is not evaluable for response. If the patient discontinues therapy due to toxicity, it will count towards the toxicity stopping rules. The patient must be followed for any unresolved toxicity per section 7.10.

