7.6 Second Treatment Course

Any patient who failed prior treatment (i.e. met section 4.2.2 of the eligibility criteria at enrollment) will have a bone marrow biopsy and aspirate performed prior to the start of the 2nd treatment course.

A second treatment course will be given 6 to 8 weeks after the start of course 1, identical to the first course substituting the frozen NK cell product for the fresh product, unless medically unsafe.

The following criteria must be met before a new treatment course is started:

- ANC recovery to baseline documented prior to course 1
- Platelet transfusion that can be managed safely in the outpatient setting

- Treatment related non-hematologic toxicity, except fatigue, alopecia, resolved to \leq grade 2
- Absence of rapid disease progression as defined in Section 7.10

If the above requirements are not met, delay and reassess weekly until recovery occurs. If more than 2 weekly delays occur (>8 weeks from the start of course 1) without hematological recovery and/or non-hematologic treatment related toxicity resolution, the patient will be taken off study. A bone marrow biopsy will be done to assess response to the therapy up to that point or to determine etiology for inadequate recovery of counts.

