7.8.4 Prolonged Marrow Suppression

Hematologic toxicity due to allogeneic NK cells may occur later, and therefore hematologic recovery will be assessed beyond the expected chemotherapy-induced nadir.

Pancytopenia will occur with this regimen and should be treated as follows:

Anemia and thrombocytopenia are expected in all patients, and they will receive standard supportive transfusion care according to transfusion committee guidelines or as modified based on clinical parameters. Prolonged anemia or thrombocytopenia are not unexpected and will not count towards toxicity.

Neutropenia is expected in the majority of patients, and they will receive supportive care with prophylactic antibiotics as noted below. G-CSF and granulocytes should be avoided unless clinically indicated in the setting of severe, uncontrolled infection. If the clinical situation warrants growth factor use, then any remaining IL-2 administration will be stopped.

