11.3 Required Reporting: Mayo Clinic to the Masonic Cancer Center

Serious events: Beginning with the first dose of decitabine and continue through day 45 of the last treatment course, as an affiliate, Mayo will report all events meeting the definition of serious, regardless of attribution or expectedness, within 24 hours of knowledge of the event. After day 45 of the last treatment course, the investigator must report upon knowledge any event that is serious, unexpected and felt to be at least possibly related to study therapy.

Reports are to be submitted to the Study Coordinator at the University of Minnesota Masonic Cancer Center (MCC) using the SAE reporting form found in OnCore. The MCC Study Coordinator will facilitate reporting to the University Of Minnesota IRB and the FDA as required.

Stopping rule events: Any grade 4 or 5 non-hematologic, non-infectious toxicity occurring through day 45 of the last treatment course will count toward the early study stopping rule per section 13 and must be reported to the MCC Study Coordinator using the Early Stopping Rule Report Form found OnCore under the reports tab.

No more than one excess toxicity event will be accumulated per patient within in the same episode of toxicity (i.e. a grade 4 event worsening to a grade 5 is a single event) or when multiple events occur concurrently.

Events that count toward an early stopping rule do not necessarily constitute a serious adverse event requiring expedited reporting and

should be reported as such only if they meet the criteria for expedited reporting as defined in section 11.1.

Lot release issues: Any safety issues associated with the final lot release at the treating institution must be reported immediately to either [name] or [name] at the University of Minnesota (contact information on page 2) with follow-up reporting to MCC Study Coordinator using the Deviation Report found in OnCore.

Affiliate institutions will be responsible for submitting reportable events to their institutional IRB and any other required local regulatory entities.

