13.2 Early Stopping Rule for Toxicities

The complications and adverse events will be closely monitored in this study. The hypothesized rate of having grade 4 or 5 non-hematologic, non-infectious toxicities for the approach is 5%. Enrollment will be stopped and the trial re-evaluated if the grade 4 or 5 toxicity rate shows signs to exceed 15%. This means enrollment will be stopped and the study re-evaluated if there are 3 patients with a non-hematologic, non-infectious grade 4-5 toxic event occurring through day 45 of the last treatment course out of the first 7 patients, 4 out of 18, 5 out of 29, 6 out of 40, and 7 patients at any time. Toxicities such as infections, including but not limited to pneumonia, bacteremia, cellulitis, and neutropenic fever, etc are known results of high risk MDS and will not be included as toxicities attributed to the study therapy. Assessment for toxicities will begin upon initiation of trial therapy and will conclude 2 weeks after last dose of study related treatment. These stopping rules of a statistical sequential probability ratio test designed for no more than 5% the probability of type I error and at least 80% statistical power.

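### Section 6.2 counts discontinuation for toxicity toward the stopping rule without limit, while 13.2 and 11.3 count only grade 4-5 non-hematologic, non-infectious events

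*Combined protocol and SAP*

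**What the plan says.** Section 6.2 covers patients who start treatment and then stop. They are replaced because they cannot be evaluated for response, and then: "If the patient discontinues therapy due to toxicity, it will count towards the toxicity stopping rules". The sentence has no grade, organ-class or infection limit and no cross-reference.

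Section 13.2 holds the only toxicity stopping rule. Its target rates are "The hypothesized rate of having grade 4 or 5 non-hematologic, non-infectious toxicities for the approach is 5" percent and, for action, "Enrollment will be stopped and the trial re-evaluated if the grade 4 or 5 toxicity rate shows signs to exceed 15" percent. The first boundary point is "3 patients with a non-hematologic, non-infectious grade 4-5 toxic event occurring through day 45 of the last treatment course" and the sequence runs "out of the first 7 patients, 4 out of 18, 5 out of 29, 6 out of 40, and 7 patients at any time". Infections, including neutropenic fever, are excluded. The stated type I error is at most 5%.

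Section 11.3 defines the reportable stopping-rule event in the same terms: "Any grade 4 or 5 non-hematologic, non-infectious toxicity occurring through day 45" of the last course. Section 11.4 refers back to section 13.

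Section 7.8.4 adds a narrower exclusion: "Prolonged anemia or thrombocytopenia are not unexpected and will not count towards toxicity".

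Two sections describe how patients come off treatment. Under 7.6, a patient more than 8 weeks from the start of course 1 "without hematological recovery and/or non-hematologic treatment related toxicity resolution, the patient will be taken off study"; the non-hematologic threshold for starting course 2 is grade 2 or lower. Section 7.10 lists unacceptable toxicity, ungraded, separately from its item on grade 4 non-hematologic toxicity.

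**The concern.** Some patients can stop for toxicity without having a 13.2 event. Examples are a treatment-related grade 3 non-hematologic toxicity that does not resolve, neutrophils that do not recover, or an ungraded unacceptable toxicity. Read as written, 6.2 adds these patients to the count; 13.2 and 11.3 leave them out. Since 6.2 can only be pointing to the 13.2 boundary, one decision rule has two event definitions.

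The boundary was derived for the rate of the 13.2 event. Adding other events to the numerator raises the counted rate with no increase in the toxicity being monitored, so the stated error rate no longer describes the rule being run. At stake is whether enrollment is paused and the study re-evaluated, and whether that decision would be the same whichever section staff follow.

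**Working it through.** **1. The conflict by example.** Suppose 3 of the first 7 patients come off for persistent grade 3 non-hematologic toxicity and none has a grade 4-5 event. Under 6.2 read literally the count is 3/7 and enrollment stops. Under 13.2 and 11.3 it is 0/7 and enrollment continues.

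**2. Reproducing the printed boundary.** Inputs from 13.2: p0 = 0.05, p1 = 0.15, type I error 0.05, power 0.80 (so beta = 0.20), sequential probability ratio test.

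- D = ln[p1(1 - p0) / (p0(1 - p1))] = ln(0.1425/0.0425) = 1.210
- slope = ln[(1 - p0)/(1 - p1)] / D = ln(0.95/0.85)/1.210 = 0.0919
- intercept = ln[(1 - beta)/alpha] / D = ln(16)/1.210 = 2.292
- largest n at which k events stop the trial = (k - 2.292)/0.0919

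For k = 3, 4, 5, 6, 7 this gives 7.70, 18.58, 29.46, 40.34 and 51.21. Rounded down: 7, 18, 29, 40 and 51. The first four match the printed points, and the last matches the 7-at-any-time limit for the maximum of 51 patients in 13.1. The boundary therefore rests on 5% versus 15% for the 13.2 event only.

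**3. Chance of stopping.** Let P(n,k) be the probability of having k counted patients after n without having stopped. Then P(n,k) = P(n-1,k)(1 - p) + P(n-1,k-1)p. After each patient, any probability at or above the boundary is removed and added to the stopping probability. The boundary is 3 for n up to 7, 4 up to 18, 5 up to 29, 6 up to 40, then 7.

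The counted rate is p = 5% + d. Here 5% is the hypothesized rate in 13.2, and d is the percentage of treated patients who have no 13.2 event but discontinue for lesser toxicity. The documents do not give d; they give only a 10% dropout from all causes (13.1). The values of d below are assumptions. The sample sizes come from 13.1: 51 enrolled at most, 46 evaluable, 17 if the trial ends at stage 1.

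| d (points) | Counted rate | 51 patients | 46 patients | 17 patients |
|---|---|---|---|---|
| 0 | 5% | 3.1% | 2.8% | 1.1% |
| 1 | 6% | 6.1% | 5.4% | 2.0% |
| 3 | 8% | 16.4% | 14.2% | 4.8% |
| 5 | 10% | 31.5% | 27.3% | 9.1% |

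With d = 0 the stated 5% limit is met. With 51 or 46 patients it is passed at one added point; with 17 patients it still holds at three.

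**The case against.** The strongest reply is that 6.2 was never meant to define an event. Its sentence directly follows the rule that a discontinued patient is replaced for response, so it may mean only that replacement does not remove the patient from toxicity monitoring. Section 13.1 says something similar: patients with partial treatment stay in the toxicity evaluation. A pointer to a stopping rule can be taken to import that rule's definition. This reading is plausible. However, the sentence makes the discontinuation itself the thing that counts, and it neither names 13.2 nor restricts the event. The ambiguity stands, and the inflation above applies only under the literal reading.

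Other objections limit how far the point can be pushed:

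- A reader might add the whole 10% dropout to the 5%, reaching a 15% counted rate and a 71% chance of stopping. The documents do not support that. Section 7.10 lists causes unrelated to toxicity, such as withdrawn consent, intercurrent illness and rapid progression, and also grade 4 non-hematologic toxicity, which is already counted.
- A reader might infer that 7.6 removes such patients often. No frequency is given.
- A reader might take 7.8.4 as a third statement of the grade 4-5 definition. It excludes only prolonged anemia and thrombocytopenia, and stopping for those is arguably not stopping for toxicity under 6.2 either. Failed neutrophil recovery and persistent grade 3 non-hematologic toxicity remain as examples, although 7.6 recognizes that poor count recovery needs its cause established.
- A reader might conclude that the two sites will report different events. Sections 11.3 and 11.4 both refer to section 13, and 6.2 carries no reporting instruction, so this is a possibility only.

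**Conclusion.** The point holds as an inconsistency in a decision rule, of moderate severity. Section 6.2 is unrestricted where 13.2 and 11.3 are specific, and the protocol's own discontinuation criteria produce patients on whom they disagree.

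The size depends on taking 6.2 literally, on a true 13.2 event rate of 5%, on the assumed share of lesser-toxicity discontinuations, and on how many patients are treated. For a full trial of 51, about one added percentage point is enough to exceed the stated type I limit; for a trial ending at stage 1 the effect is much smaller. It would go too far to say that the plan's type I error fails: under the 13.2 definition it is met, at 3.1%. The harm is also bounded. Crossing the boundary leads to a pause and re-evaluation, at which the triggering events would be visible. Over-counting hides no grade 4-5 event and does not alter the response analysis.

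**What to change.** Reconcile 6.2 with 13.2 and 11.3 so that the boundary has one event definition. Which definition is intended is for the sponsor to state.

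- If 13.2 governs, amend 6.2 to say that a discontinuation counts when the event meets the 13.2 definition and that the patient stays in the toxicity count after replacement. Report all other toxicity discontinuations separately to the Data and Safety Monitoring Council. This costs one sentence and a line on the stopping-rule form, and leaves the boundary and its error rates unchanged. The downside is that fewer discontinuations trigger the automatic pause; the separate listing partly offsets this.
- If every toxicity discontinuation is meant to count, put that in the 11.3 and 13.2 definition, reconcile 7.8.4 with it, restate the acceptable and unacceptable rates for the wider event, and re-derive the boundary. This is a larger amendment and needs a justified rate for the wider event, which the documents do not now contain.

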7.0 Treatment Plan

Treatment is planned to be given in the outpatient setting and must begin on a Monday to avoid weekends. The administration of the study drugs will follow institutional drug and supportive care guidelines. There will be no dose escalation or de-escalation except for IL-2 where modifications are allowed for unacceptable toxicity.

Study Day	Days of Week	Study Drug	Section of protocol
Days 1-5	Monday-Friday	Decitabine 10 mg/m ² IV	Section 7.1
Days 6-15	Saturday through the 2 nd Monday	Vorinostat 200 mg PO twice a day	Section 7.2
Day 15	Monday	Donor apheresis (course 1 only)	Section 7.3
Day 16	Tuesday	Patient – rest	Section 7.2
Day 17	Wednesday	NK cell infusion	Section 7.4
Days 17, 19, 22	Wednesday, Friday, Monday	IL-2 6 MU SQ beginning 2 hours after the NK cell infusion for 3 doses	Section 7.5

Repeat the treatment course 6 to 8 weeks later unless medically unsafe. Requirements for proceeding to course 2 are defined in Section 7.6.

Clinical response will be formally assessed 4 - 6 weeks after the 2nd course based on International Working Group (IWG) criteria (Appendix VI); however a bone marrow evaluation will be done if the patient is taken off treatment early.

7.1 Decitabine (Days 1-5)

Decitabine 10 mg/m² will be administered as a 1 hour intravenous infusion days 1 through 5.

7.2 Vorinostat Administration (Days 6-15)

Vorinostat will be taken at a dose of 200 mg (daily dose of 400 mg) twice daily with food for 10 days. The capsules must be swallowed whole. If a Vorinostat capsule is accidentally opened or crushed, the capsule or the powder must not be touched. Patients will be provided with a daily drug log (appendix VIII) to record their vorinostat dosing as well as any side effects.

Day 16 is a rest day with no treatment.

7.3 Donor Apheresis (Day 15 Course 1 Only) and Cell Product Manufacturing

Peripheral blood cells will be collected by a single apheresis from the haploidentical related donor on day 15 of course 1 only (Monday). Apheresis collections will be performed on the Amicus Apheresis system (Fenwal Inc., Lake Zurich IL, USA) and will use a fixed time of 5 hours with a flow rate of 65 ml/min. The cycle volume of 1400 ml (manufacturer recommendation) will be used. Anticoagulant will consist of either ACD-A or heparin/ACD-A.

Cell product manufacturing will be performed at the University of Minnesota Molecular and Cellular Therapeutics (MCT) laboratory. Mayo Clinic will utilize overnight courier services.³⁹ The apheresis product and a tube of donor blood (2ml EDTA) will be sent from Mayo Clinic by overnight courier the day of collection (day 15). Refer to the Affiliate Laboratory Manual regarding shipping specifics.

At MCT, the apheresis product will be enriched for NK cells with the large-scale CliniMacs device (Miltenyi) by depletion of CD3+ cells to remove T-lymphocytes and depletion of CD19+ cells to remove B-lymphocytes. The NK cell product will then be divided in two with half stored frozen at MCT until day 17 of course #2.

The remaining NK cell enriched product will be activated by incubation with 1000 U/ml IL-2.

For U of MN patient products, the cells with IL-2 will be processed with lot release testing per the CMC but held for infusion until the morning of day 17.

For Mayo patient products, the cells with IL-2 will be shipped to Mayo's cell product lab on day 16 by overnight courier for arrival the morning of day 17. Partial lot release testing on the pre-IL-2 product including sterility testing (Gram stain, endotoxin), cell viability, flow cytometry analysis will be performed prior to shipping the cells to Mayo. Results will be confirmed with Mayo prior to the NK cell product infusion.

At Mayo, the cells will be washed and final lot release performed.

Samples for TTL in association with original cell production/infusion #1:

A sample of the cell product will be sent from MCT to the Masonic Cancer Center's Translational Therapy Lab (TTL) for cell function and phenotype studies from the following samples:

- 1) the apheresis unit before processing (100×10^6 cells)
- 2) the post-column pre IL-2 incubation sample (10×10^6 cells)
- 3) the final IL-2 product (10×10^6 cells)

Course #2

The frozen NK cells will be thawed by MCT on day 16 and incubated with IL-2. For Mayo patients, the cells with IL-2 will be shipped to Mayo's cell product lab by overnight courier for arrival the morning of day 17. On day 17, the institutional cell product laboratory will wash and release for infusion according to the CMC for infusion on day 17 of the 2nd treatment course.

Samples for TTL in association with infusion #2:

A sample of the cell product will be sent to the Masonic Cancer Center's Translational Therapy Lab (TTL) at the following time points:

- 1) the post thaw, pre IL-2 incubation sample (10×10^6 cells)
- 2) the final IL-2 product (10×10^6 cells)

Refer to the chemistry, manufacturing and control (CMC) section of the Investigational New Drug (IND) application for additional preparation information and lot release criteria.

7.4 Allogeneic CD3⁻ CD19⁻ Selected NK Cell Product Infusion (Day 17)

Pre-medication: Patients should be pre-medicated with acetaminophen 650 mg PO and/or diphenhydramine 25 mg PO/IV within 1 hour before and 4 hours after the NK cell infusion. Demerol 25-50 mg IV may be given for chills/rigors during the NK cell infusion. Corticosteroids must not be used.

Infusion guidelines: The NK cells will be infused without a filter or pump, slowly by gravity over at least 15 minutes but no longer than 1 hour. The targeted infused cell dose of CD3⁻ CD19⁻ selected NK cell product is within the range of 2-3 x 10⁷ cells/kg. However, cell infusion will proceed regardless of cell dose if prior defined product collection parameter of > 3-fold NK cell enrichment between the apheresis and final products is met. Flush tubing on completion of the NK cells with normal saline to ensure all of the cells are infused.

Vitals: Obtain vital signs before the NK cell infusion, every 15 minutes during the infusion, and then every 30 minutes x 2, then pre routine. Monitoring time will total at minimum 2 hours after NK cell infusion.

Monitoring: Patients will be monitored for adverse effects of the NK cell infusion such as rash, acute allergic reaction, bronchospasm, respiratory distress, and acute vascular leak syndrome. If life threatening acute reactions occur (defined as CTCAE grade 4 - life-threatening consequences; urgent intervention indicated), the infusion will be stopped. If grade 4 infusion reaction occurs refer to section 8.1.3 regarding testing for HAMA.

Hydration will be administered per institutional guidelines. Any elevation of metabolic monitoring will be treated with more aggressive hydration, while being attentive to fluid overload.

Corticosteroids are to be avoided from the time of NK cell infusion through day 25. If essential, low doses of steroids (e.g. 25 mg hydrocortisone) may be given as clinically indicated during this window.

7.5 IL-2 (begin day 17)

Start subcutaneous IL-2 approximately 2 hours, but no earlier than 2 hours, after the NK cell infusion in the absence of grade 4 infusion related toxicity.

If the patient has experienced grade 4 infusion related toxicity and it resolves to grade 2 or better, the IL-2 may be started up to 48 hours after the NK infusion. If no IL-2 is given, the patient will be replaced for statistical analysis.

IL-2 administration: IL-2 will be given at 6 million units on days 17, 19 and 22. For patients weighing less than 45 kilograms, the IL-2 will be given at a dose of 3 million units/m² on days 17, 19 and 22. For the purposes of outpatient scheduling and/or possible delay in treatment start, dosing may be altered to avoid weekends as long as IL-2 is not given on consecutive days and completed within a week.

Pre-medication with acetaminophen 650 mg PO and diphenhydramine 25 mg PO/IV before and 4 hours after each dose of IL-2 is recommended.

Monitoring during IL-2 administration: Patients are monitored for IL-2 related toxicities on a daily basis in clinic until the day after the final IL-2 administration with increased monitoring as clinically required.

IL-2 dose-adjustment for individual patient intolerance: Fevers, rash and flu-like symptoms are expected and should be treated supportively with acetaminophen and diphenhydramine as described above. If a patient cannot tolerate full dose IL-2 due to fevers, rash or constitutional symptoms, a dose decrease to 4 million units is allowed (2 million units/m² if < 45 kg). If the patient cannot tolerate the reduced dose, the IL-2 must be permanently discontinued.

IL-2 dosing guidelines for non-hematologic grade 3-4 toxicity (CTCAE v4):

Non-hematologic grade 3 toxicity persisting for > 24 hours: Hold IL-2. If the toxicity resolves to grade 2 or better within 48 hours, the IL-2 can be resumed at a reduced dose (4 million units or 2 million units/m² if < 45 kg). If the same toxicity persists, worsens or recurs, the IL-2 must be permanently discontinued. Missed doses are not made up.

Non-hematologic grade 4 toxicity: Permanently discontinue IL-2

